7.4.8 Subgroup Analyses of the Secondary Efficacy Endpoints

The secondary efficacy endpoints HAM-A and SHAPS will be summarized using the following subgroups:

- HAM-A total score will be presented by baseline SHAPS score (< median and ≥ median).
- SHAPS score (both SHAPS Total Score [14 to 56] and SHAPS Original Total Score [0 to 14]) will be presented by baseline

Summaries by subgroup will only be produced if there are at least 20 subjects in the category of interest. Additional subgroup analyses may be performed post-hoc, as appropriate.

	I		

Confidential

Confidential

7.4.10 Interim Analyses and Data Monitoring

There are no interim analyses planned.

7.4.11 Additional supportive analyses to assess impact of COVID-19

Efficacy Endpoints Ascertainment

In the event that a subject cannot come to the clinic after the baseline visit due to selfquarantine, local restrictions, illness, or other reasons as described in the protocol, the site personnel may conduct a virtual (by telephone contact) visit. A table summarizing the mode of ascertainment of efficacy endpoints (in-clinic vs. phone) will be presented by treatment assignment, type of efficacy assessment and visit.

A listing will also be provided. The impact of the efficacy endpoints ascertainment (inperson vs. phone) will be explored in additional analyses if a large imbalance in ascertainment method between treated and placebo is present at study visits.

Study Discontinuation

Reasons for study discontinuation identified by the investigator as related to COVID-19 will be listed.

7.5 Safety Evaluation

Safety analysis will be carried out for the Safety Population, to include all subjects who receive at least one dose of study drug. Safety analyses will include data for each subject during the treatment-emergent period (from first dose of study drug to 30 days after last dose) except for the summary of AESIs. Subjects who do not complete the study, for whatever reason, will have all available data up until the time of termination included in the analysis.

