- ^g At Screening, collect height for BMI calculation.
- ^h Ophthalmologic examinations will be performed by a site-affiliated ophthalmologist. Details for the standard ophthalmologic examination and corneal specular microscopy will be described in a separate ocular monitoring manual. Additional standard ophthalmologic exams and / or corneal specular microscopies may be conducted to assess subject safety.

BTRX-335140 Clinical Study Protocol Amendment 7

- ⁱ Baseline ophthalmologic examinations (standard and corneal specular microscopy) must be performed before randomization.
- ^j Prior to Visit 3 (Week 2) (between Days 7 and 14 [+2 days]), a standard ophthalmologic examination will be performed.
- ^k Serum pregnancy test is to be performed at screening visit only and urine pregnancy tests will be performed by the site at all subsequent visits.
- ^m Optional assessment; subject refusal to perform will not prohibit study participation.
- ⁿ Unscheduled hepatic monitoring testing may be performed at any time on the basis of clinical laboratory testing results, after consultation with the Sponsor-designated medical monitor (see Section 6.3.2.2).
- ^o The C-SSRS Baseline version will be used at Screening and "Since Last Visit" version will be used for all subsequent visits.
- ^p Adverse events reported before first dose of study drug to be recorded as medical history. Serious AEs will be recorded on the AE eCRF from the time of informed consent.
- ^q Subjects will be instructed to take their study drug daily in the morning and preferably with food.
- ^r Subjects will take their first dose of study drug (BTRX-335140 or placebo) under the supervision of clinical study personnel during the baseline visit.
- s
- ^t The Week 12 corneal specular microscopy should be completed for all subjects (ie, completers and early termination) unless consent is withdrawn. The corneal specular microscopy should be conducted approximately 12 weeks after the first dose of study drug; exceptions to be discussed with the medical monitor.

BTRX-335140	BlackThorn Therapeutics, Inc.
Clinical Study Protocol Amendment 7	Date: 24Jan2022

TABLE OF CONTENTS

CL	INICAL ST	TUDY PROTOCOL: K2-MDD-201	1
SP	ONSOR SI	GNATURE	2
IN	VESTIGAT	FOR AGREEMENT	3
SU	MMARY (OF CHANGES	4
SY	NOPSIS		5
SC	HEDULE (OF PROCEDURES AND ASSESSMENTS	11
TA	BLE OF C	ONTENTS	14
LIS	ST OF TAE	BLES	
LIS	ST OF FIG	URES	
LIS	ST OF APP	ENDICES	
LIS	ST OF ABE	BREVIATIONS	19
1	IN	TRODUCTION	
	1.1	Background Information	

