Subjects who meet the DSM-5 diagnostic criteria for MDD and all other eligibility criteria for the study will be randomized in a 1:1 ratio to 1 of 2 treatment arms (placebo or BTRX-335140 QD) until approximately 180 subjects are randomized. Beginning at Visit 2 (Baseline), subjects will receive treatment with BTRX-335140 80 mg QD or placebo for 8 weeks. During the Safety Follow-up, all subjects will receive a telephone call (TC) from study site personnel approximately 2 weeks after discontinuation of study drug for assessment of AEs, concomitant medication usage, and C-SSRS; and at Week 12, subjects will have corneal specular microscopy performed by a study site-affiliated ophthalmologist. The overall duration in the study for each subject is expected to be approximately 14 to 16 weeks.

The Week 12 corneal specular microscopy should be completed for all subjects (ie, completers and early termination) unless consent is withdrawn. The corneal specular microscopy should be conducted approximately 12 weeks after the first dose of study drug; subjects who terminate the study early would need to plan for the corneal specular microscopy at 12 weeks after the first dose of study drug. Any exceptions are to be discussed with the medical monitor.

Additional ophthalmologic examinations (standard ophthalmologic exams and/or corneal specular microscopies) may be conducted to assess subject safety.

Details of study procedures and assessments are provided in Section 6; for details on the timings of study assessments refer to Section 7 and the Schedule of Procedures and Assessments.

Study sites will maintain, at a minimum, coronavirus disease 2019 (COVID-19) risk mitigation procedures as per regulatory and local guidelines and/or laws. Allowed modifications to the conduct of the study, in the event of site staff and/or patient restrictions due to COVID-19, are outlined in Appendix 1.

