6.4.2.8 Ophthalmologic Examination

The following ocular assessments are performed, using these standard clinical operating procedures, at specified visits, on both eyes of each subject:

- 1. Standard Ophthalmologic Examinations: performed at Screening/Baseline, between post-dose days 7-15, and at end of treatment/Week 8.
- 2. Corneal Specular Microscopy (CSM): noncontact or contact specular microscopy for qualitative and quantitative examination of the central corneal endothelium (cell count, cell shape, density, and morphology), with image capture at Screening/Baseline and 12 weeks following first dose.

Local investigators assess and record the results of items 1 and 2 on the examination worksheet. For both the standard ophthalmologic examination and CSM, an assessment of normal/abnormal is captured as well as whether the abnormal result is clinically significant or not. CSM results are sent to **second second** where the designated ophthalmology expert will review. Additional ophthalmologic examinations (standard ophthalmologic exams and/or corneal specular microscopies) may be conducted at any time during the study to assess subject safety.

The final ocular examination for corneal specular microscopy is conducted approximately 12 weeks (+2 days) after the first dose of study drug (including both subjects who complete the study and subjects who discontinue early from the study).

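### SAP Section 7.5 and SAP Table 4 disagree on whether the Week 12 corneal specular microscopy enters the safety summaries; read literally, 7.5 would drop it for subjects who stop dosing early

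*SAP*

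**What the plan says.** **The general limit.** SAP Section 7.5 says: "Safety analyses will include data for each subject during the treatment-emergent period (from first dose of study drug to 30 days after last dose"; the only carve-out is "except for the summary of AESIs". The next sentence says that subjects who do not complete "will have all available data up until the time of termination included in the analysis".

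**The timing of the image.** SAP Section 6.4.2.8 plans microscopy "with image capture at Screening/Baseline and 12 weeks following first dose", and says that the final examination "is conducted approximately 12 weeks (+2 days) after the first dose of study drug", for completers and for those who discontinue early. Protocol Section 3.1 says that "subjects who terminate the study early would need to plan for the corneal specular microscopy at 12 weeks after the first dose of study drug". Protocol Schedule of Procedures, footnote t, adds: "The Week 12 corneal specular microscopy should be completed for all subjects (ie, completers and early termination) unless consent is withdrawn".

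**The specific window.** SAP Section 7.1.2 maps by-visit safety assessments to Table 4. There the microscopy row has a single post-baseline window, Week 12, defined as Day ≥2 with no upper end. The rows for vital signs, laboratory tests, COWS, body weight, ECG and C-SSRS each end at last dose + 30.

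**The outputs.** SAP Section 7.5.5.3 plans a shift table from baseline to end of study. It also plans summaries of central-reader cell density and coefficient of variation, and counts of subjects with cell-density loss of at least 5%, 10% and 15%. The SAP addendum changes the Table 4 row for the standard eye examination and presents the shift summary by visit. It changes neither the microscopy window nor the limit in 7.5.

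**The concern.** One clock runs from first dose (the image) and the other from last dose (the limit on safety data). They agree only for subjects who dose for nearly the full eight weeks. The earlier a subject stops, the further the Week 12 image falls beyond last dose + 30.

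The two rules can also be applied in sequence. Table 4 assigns an assessment to a named visit, and Section 7.5 says which data enter a safety analysis. A programmer could map the image to Week 12 and then drop it. Because 7.5 names one exemption and microscopy is not it, that would be a defensible literal reading.

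At stake are the cell-density, coefficient-of-variation, percentage-loss and shift tables. Under the literal reading they would hold mainly subjects with near-complete dosing and would omit those who stopped early, including any who stopped for tolerability. That selection depends on events after randomisation. The protocol makes a point of bringing these subjects back for imaging, and Protocol Section 8.4 bases the events of special interest partly on nonclinical ocular phototoxicity.

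**Working it through.** **Inputs**
- First dose is Day 1 (SAP Section 7.1.4).
- Image: "approximately 12 weeks (+2 days) after the first dose of study drug" (SAP Section 6.4.2.8).
- Limit: last dose + 30 days (SAP Section 7.5).
- Visit 6: Day 57 ± 2, that is Day 55 to 59 (SAP Table 4).
- The documents do not settle whether a dose is taken on the Visit 6 day. Assumption: the last dose of a completer is on that day or the day before.

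**Step 1. Reproduce the plan's own day.** Week k falls on Day 1 + 7k. Week 8 is 1 + 56 = Day 57 and Week 12 is 1 + 84 = Day 85; both match Table 4. Adding the 2-day allowance gives Day 85 to 87.

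**Step 2. Exclusion rule under a literal 7.5.** With examination day C and last-dose day L, the image is excluded if C > L + 30.
- The whole window is lost if 85 > L + 30, that is L ≤ 54.
- None of it is lost if 87 ≤ L + 30, that is L ≥ 57.

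**Step 3. By last-dose day**

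| Last dose (L) | Limit (L + 30) | Examination days excluded |
|---|---|---|
| Day 15 | Day 45 | 85, 86, 87 (Day 85 is 40 days too late) |
| Day 29 | Day 59 | 85, 86, 87 (26 days too late) |
| Day 43 | Day 73 | 85, 86, 87 (12 days too late) |
| Day 54 | Day 84 | 85, 86, 87 (1 day too late) |
| Day 55 | Day 85 | 86, 87 |
| Day 56 | Day 86 | 87 |
| Day 57 or later | Day 87 or later | none |

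**Step 4. Completers within the visit windows.** Five Visit 6 days and three examination days give 5 × 3 = 15 combinations.
- Last dose on the visit day (L = 55 to 59): 2 + 1 + 0 + 0 + 0 = 3 of 15 excluded.
- Last dose the day before (L = 54 to 58): 3 + 2 + 1 + 0 + 0 = 6 of 15 excluded.

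These count calendar combinations. The documents give no distribution of visit days, so they are not shares of patients.

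**Step 5. Nominal schedule.** With L = 56 or 57 the limit is Day 86 or 87, and an examination on Day 85 is inside it. Nothing is lost.

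**Step 6. Table 4 alone.** Days 85, 86 and 87 all satisfy Day ≥2, so no image is excluded for any last-dose day.

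**The case against.** The strongest reply is that the specific rule governs and already keeps every image. Table 4 writes last dose + 30 into six kinds of assessment and leaves it out of both ocular rows, which looks deliberate. The addendum reaffirms Table 4 for by-visit safety analyses and presents the ocular shift summary by visit. Section 7.5.5.3 runs that shift to end of study, not to a limit after last dose.

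Section 7.5 also cannot be an exhaustive filter. Taken literally, a period starting at first dose would remove every pre-dose baseline and the screening C-SSRS summary planned in Section 7.5.5.7. Section 7.5.3 lists deaths in the post-treatment follow-up although only events of special interest are exempted. The sentence on non-completers is inclusive; it does not say that later data are dropped.

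Much of this stands. It makes retention the more likely intention, and it rules out saying that the SAP removes the images. It does not settle the matter. Nothing states that Table 4 prevails over 7.5, and naming a single exemption invites the inference that everything else is limited. The by-visit statement in the addendum covers the shift summary, not the cell-density and coefficient-of-variation tables. The sentence on non-completers does not clearly bring in an image taken after termination.

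Two further points also stand. Central-reader results are listed, and listings are not windowed, so the data stay visible; a listing does not, however, replace a comparison by arm. Unscheduled microscopy is allowed at any time, and an image within the limit would be kept.

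**Conclusion.** This is an unresolved conflict inside the SAP, with selective loss of data as the consequence of one reading. Under that reading the only scheduled post-baseline image leaves the summaries for every last dose on or before Day 54, and for last doses on Day 55 or 56 when the examination falls late in its window. Under the other reading nothing is lost.

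A reader might infer that the SAP discards the microscopy of all early terminators. The documents do not support that: it requires 7.5 to override Table 4, a last dose by Day 54, and an examination on Day 85 to 87. The timing is approximate, and exceptions may be discussed with the medical monitor. A reader might also take 3 of 15 and 6 of 15 as 20% and 40% of completers lost. They are counts of day combinations, and on the nominal schedule the loss is zero.

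The day arithmetic is exact given the stated windows. How many subjects would be affected cannot be derived from the documents. The point deserves correction because the subjects at risk of omission are the early stoppers whom the protocol takes care to image.

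**What to change.** Add one sentence to SAP Section 7.5: corneal specular microscopy and the standard ophthalmologic examination follow their windows in Table 4, as amended by Table 2 of the addendum, and are exempt from the 30-day limit and from any cutoff at study termination. All Week 12 images, including those of early terminators, then enter the summaries of Section 7.5.5.3. The standard examination belongs in the same sentence because its Week 8 window (Day ≥15) is also open-ended.

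Show days since last dose in the microscopy listing, so that a reader can see how long after treatment each image was taken.

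The cost is one sentence and one derived listing column, with no new data and no change to the examination schedule. The choice should be in writing before unblinding, so that it cannot depend on the results. If that is no longer possible, the rule actually applied should be stated in the clinical study report.

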7.5.1 Adverse Events

TEAEs are defined as those AEs with onset after the first dose of study drug or existing events that worsened after the first dose during the study and that occur prior to 30 days after last dose of treatment. TEAEs will be summarized by treatment group. Events reported with a partial onset date (e.g., month and year are reported but the day is missing) will be considered to be treatment-emergent unless a partial date clearly indicates that it occurred prior to first dose of study treatment or more than 30 days after last dose of treatment.

Verbatim terms on case report forms will be mapped to preferred terms and system organ classes using MedDRA version 22.1.

Summaries that are displayed by system organ class and preferred terms will be ordered by descending incidence of system organ class and preferred term within each system organ class. Summaries displayed by preferred term only will be ordered by descending incidence of preferred term. Summaries of the following types will be presented:

- Overall summary of number of unique TEAEs and treatment-emergent serious adverse events (TESAEs) and subject incidence of TEAEs meeting various criteria;
- Subject incidence of TEAEs by MedDRA system organ class and preferred term;
- Subject incidence of TEAEs by MedDRA preferred term;
- Subject incidence of TEAEs by severity grade, MedDRA system organ class, and preferred term;
- Subject incidence of TEAEs related to study drug, MedDRA system organ class, and preferred term;
- Subject incidence of TEAEs related to study drug by MedDRA preferred term;
- Subject incidence of TEAEs leading to discontinuation of study drug by MedDRA system organ class and preferred term;
- Subject incidence of severe TEAEs related to study drug by MedDRA system organ class and preferred term;
- Subject incidence of SAEs by MedDRA system organ class and preferred term;
- Subject incidence of AESIs by MedDRA system organ class and preferred term.
- Subject incidence of AESIs by severity grade, MedDRA system organ class, and preferred term; and

BlackThorn Therapeutics, Inc.	Statistical Analysis Plan
K2-MDD-201	Version 2.0; 03 June 2022

• Subject incidence of AESIs related to study drug, MedDRA system organ class, and preferred term

7.5.3 Deaths, Other Serious Adverse Events, and Other Significant Adverse Events

All deaths during the study, including the post treatment follow-up period, will be listed by treatment group and subject, to include the primary cause of death. Treatmentemergent serious AEs and other significant AEs, including those that led to discontinuation of the study drug, will be provided in separate subject data listings.

7.5.4 Clinical Laboratory Evaluation

All descriptive summaries of laboratory results will be based on data analyzed by the central laboratory and presented in Système International (SI) units, as suggested by the Center for Biologics Evaluation and Research and the Center for Drug Evaluation and Research *Position on Use of SI Units for Lab Tests* (Oct 2013). All data will be included in by-subject data listings. Laboratory measurements identified as abnormal (ie, outside the normal range) will also be listed separately.

BlackThorn Therapeutics, Inc.	Statistical Analysis Plan
K2-MDD-201	Version 2.0; 03 June 2022

Clinical laboratory measurements, including serum chemistry and hematology, will be summarized by treatment group. Descriptive statistics will be presented for observed values and changes from baseline at each visit where parameters were scheduled to be collected per the clinical study protocol.

Where applicable, laboratory results will be classified as "low," "normal," or "high" with respect to the parameter-specific reference ranges (ie, below the lower limit of the normal range, within the normal range, or above the upper limit of the normal range). Three-by-three contingency tables will be presented for each laboratory parameter to summarize the shift from the baseline category to the worst post-baseline measurement, defined as the value numerically farthest outside of the normal range across all post-baseline visits through the end of the study. Summary results will include the count and percentage of subjects within each shift category and treatment group.

The number and percentage of subjects with a PCS (potentially clinically significant) laboratory result for the select analytes listed below in

will be presented by treatment group and study visit. PCS laboratory results will also be listed.

Analyte	PCS Cutoffs
Hemoglobin	Low:< 10.0 g/dL; < 6.2 mmol/L; <100 g/L
	High: > 2 g/dL (20 g/L) above ULN or above baseline if
	baseline is above ULN
Platelets count	<75,000/mm3; <75.0 x 10e9 /L
WBC count	<3000/mm3; <3.0 x 10e9 /L
Neutrophils	<1500/mm3; <1.5 x 10e9 /L
Lymphocytes	Low: < 800/mm3; < 0.8 x 10e9 /L
	High: >4000/mm3 - 20,000/mm3; > 4 x 10e9 /L - 20 x 10e9 /L
Total bilirubin	> 1.5 x ULN
AST	> 3.0 x ULN
ALT	> 3.0 x ULN
Alkaline phosphatase	> 3.0 x ULN
Creatinine	> 1.5 x above baseline; > 1.5 x ULN
Sodium	Low: < 130 mmol/L
	High: > 150 mmol/L
Potassium	Low: < 3.0 mmol/L
	High: > 5.5 mmol/L
СК	> 5 x ULN
GGT	>2.5 x ULN
BUN	> 30 mg/dL; > 10.71 mmol/L

Table 5 Potentially Clinically Significant Laboratory Results

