6 INVESTIGATIONAL PLAN

6.1 Overall Study Design

Study K2-MDD-201 is a US-based, randomized, double-blind, placebo-controlled, parallel-group, multicenter study to evaluate the effects of BTRX-335140 on symptoms of depression in approximately 180 adult subjects with MDD and symptoms of anhedonia and anxiety after 8 weeks of double-blind treatment. The study consists of a 7- to 28-day screening period, an 8-week active treatment period (during which subjects will receive either BTRX-335140 or placebo), and a 4-week safety follow-up period.

Subjects sign an informed consent form (ICF) and then enter the screening period to ensure they meet the required inclusion and exclusion criteria, including diagnosis and stability of depressive symptoms and absence of psychiatric and medical conditions that would preclude study participation. The 28-day screening period may be extended to 35 days (after consultation with and approval by the medical monitor), if necessary, for reasons including, but not limited to, discontinuation of a subject's current inefficacious medications or to obtain an ophthalmologic examination.

Subjects who meet the Diagnostic and Statistical Manual of Mental Disorders Fifth Edition (DSM5) diagnostic criteria for MDD with symptoms of anhedonia and anxiety and all other eligibility criteria for the study are randomized in a 1:1 ratio to 1 of 2 treatment arms (placebo or BTRX-335140 once daily [QD]). Beginning at Visit 2 (Baseline), subjects receive treatment with BTRX-335140 80 mg QD or placebo for 8 weeks. Scheduled visits take place every two weeks (Week 2, 4, 6, and 8). During the Safety Follow-up, all subjects receive a telephone call from study site personnel for assessment of AEs, concomitant medication usage, and Columbia Suicide Severity Rating Scale (C-SSRS). The overall duration in the study for each subject is approximately 14 to 16 weeks.

Efficacy and safety endpoints are described in Section 6.4 and are measured according to the Schedule of Assessments described in Appendix A: Schedule of Procedures and Assessments.

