6.4.2.4 Laboratory Parameters

A central laboratory will be used for safety laboratory tests. Standard clinical laboratory tests are performed at times specified in the Schedule of Procedures and Assessments section of the clinical study protocol. Repeat testing of samples may be permitted during screening, after review and approval by the medical monitor.

BlackThorn Therapeutics, Inc.	Statistical Analysis Plan
K2-MDD-201	Version 2.0; 03 June 2022

Abnormal laboratory values are graded by the investigator as "clinically significant" or "not clinically significant," where applicable. Clinically significant abnormal laboratory values will be reported as AEs. Investigators may repeat laboratory tests for any parameter that is abnormal and/or clinically significant.

Table 2 lists the specific laboratory analyses that will be performed for this study.

Hematology ^a :	Chemistry ^a : Serum concentrations of:
Hemoglobin	Sodium
Hematocrit	Potassium
Erythrocyte count (red blood cell [RBC])	Bicarbonate
Mean cell volume (MCV)	Chloride
Mean cell hemoglobin concentration (MCHC)	Total bilirubin
Leukocytes (white blood cell [WBC])	Direct bilirubin
Neutrophils, segmented	Alkaline phosphatase
Absolute Neutrophil Count (ANC)	Alanine aminotransferase/serum glutamic pyruvic
Lymphocytes	transaminase (ALT/SGPT)
Monocytes	Aspartate aminotransferase/serum glutamic oxaloacetic transaminase (AST/SGOT)
Eosinophils	Gamma-glutamyl transferase (GGT)
Basophils	Blood urea nitrogen (BUN)
Platelets	Creatinine
Prothrombin time ^b	Uric acid
Urinalysis ^a :	Phosphorous
Specific gravity	Calcium
рН	Glucose (random)
Protein	Albumin
Glucose	Total cholesterol
Ketones	Creatine kinase (CK) ^c
Blood	Magnesium
Urine leukocyte esterase	Amylase
Urobilinogen	Lipase
Urine Drug Screen and Breathalyzer Alcohol	Viral Serology ^d
Screen ^a	Hepatitis B Surface Antigen (HBs Ag)
Amphetamines	Hepatitis B Core Antibody (HBc Ab)
Barbiturates	Hepatitis C Antibody (HC Ab)
Benzodiazepines	Hepatitis A Antibody (HAV-Ab [IgM])
Delta-9-tetrahydrocannabinol (THC)	Human immunodeficiency virus (HIV)
Cocaine	
Ethyl alcohol (via breathalyzer)	
Opioids	

Table 2Clinical Laboratory Tests

Phencyclidine	
Propoxyphene	
Methadone	
Thyroid function ^d :	
Thyroid-stimulating hormone (TSH); if abnormal perform Free T3 and Free T4 reflex testing	
Pregnancy Test (females of child bearing	
potential only) ^e	

^a Performed at each visit.

- ^b To be conducted at baseline only, unless indicated for hepatic monitoring testing

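### The laboratory shift table keeps one worst value per subject and analyte, so a subject with both a low and a high value is shown in one direction only

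*SAP*

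**What the plan says.** SAP Section 7.5.4 (Clinical Laboratory Evaluation) sets the display: "Three-by-three contingency tables will be presented for each laboratory parameter to summarize the shift from the baseline category to the worst post-baseline measurement". The worst measurement is "defined as the value numerically farthest outside of the normal range across all post-baseline visits through the end of the study". The counting unit is the subject: "Summary results will include the count and percentage of subjects within each shift category and treatment group". The section has no separate lowest and highest value, does not scale the distance to the limit that was crossed, and gives no tie rule. The SAP addendum leaves this part unchanged.

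The same section plans other laboratory outputs:

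- descriptive statistics for observed values and changes, by visit;
- a listing of every out-of-range value: "Laboratory measurements identified as abnormal (ie, outside the normal range) will also be listed separately";
- counts of PCS results, which "will be presented by treatment group and study visit. PCS laboratory results will also be listed".

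Table 5 has a low cut-off for seven analytes: hemoglobin, platelets, WBC, neutrophils, lymphocytes, sodium ("Low: < 130 mmol/L") and potassium.

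**The concern.** A shift table is read as subject incidence: how many subjects moved to Low, and how many to High, in each arm. That reading needs a subject who did both to be counted in both. Here such a subject falls in one post-baseline column and the other excursion leaves the table.

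The choice of column also depends on measurement scale. A value cannot fall further below the range than the lower limit itself (LLN), since it cannot go below zero. The distance above the upper limit (ULN) has no such bound. For an analyte with a long right tail and a lower limit near zero, the high excursion will therefore tend to win.

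At stake is the accuracy of a descriptive safety table. No test or decision rule depends on it.

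**Working it through.** The documents state no figure on this point, so there is none to reproduce. The first step follows from the rule alone. The other two are illustrations on stated assumptions.

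**Inputs from the documents.** One worst value per subject and parameter, on raw distance (SAP 7.5.4). Four post-baseline laboratory visits: Weeks 2, 4, 6 and 8 (SAP 6.1), with hematology and chemistry "Performed at each visit" (SAP Table 2). About 180 subjects randomized 1:1 (protocol 3.1), so 180 / 2 = 90 per arm.

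**Step 1: the rule.** Let D_low = LLN − lowest post-baseline value and D_high = highest post-baseline value − ULN. If both are positive, the subject is shown as High when D_high > D_low and as Low when D_low > D_high. Since D_low cannot exceed LLN, any value above ULN + LLN hides every possible low value. With an assumed neutrophil range of 1.8 to 7.7 ×10⁹/L, that bound is 7.7 + 1.8 = 9.5. For example, visits at 1.2, 4.0, 9.0 and 5.0 give D_low = 1.8 − 1.2 = 0.6 and D_high = 9.0 − 7.7 = 1.3. The subject is shown as High and the 1.2 is absent from the table.

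**Step 2: neutrophil example.** Assumptions: log-normal values, median 4.0, range 1.8 to 7.7, between-subject log SD 0.25, four visits, simulated.

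| Within-subject log SD | Single values out of range | Subjects with any low | Of these, shown as High | Of subjects with any high, shown as Low | Hidden lows per arm of 90 |
|---|---|---|---|---|---|
| 0.25 | 4.4% | 3.9% | 0.05% | under 0.01% | 0.002 |
| 0.35 | 9.6% | 10.6% | 2.3% | 0.2% | 0.2 |
| 0.45 | 16.2% | 20.0% | 10.0% | 1.1% | 1.8 |

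The last column is 90 × (subjects with any low) × (share shown as High). In the bottom row this is 90 × 0.200 × 0.100 = 1.8. Among subjects with both excursions, the low one was dropped in about 85% in the two lower rows; in the top row such subjects are too rare to matter. If a reference range is meant to cover the central 95% of values, about 5% should fall outside it. Only the first row is near that.

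**Step 3: other distribution shapes.** Assumptions: the range covers the central 95% of the population; the within-subject share of variance is 0.3, 0.6 or 0.9; the within-subject SD on study is unchanged or raised 1.5-fold; four visits.

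Share of two-directional subjects whose low value is the one dropped:

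- symmetric: about 50%;
- log-normal, log SD 0.2: about 70 to 74%;
- log-normal, log SD 0.4: about 84 to 88%;
- log-normal, log SD 0.6: about 90 to 95%;
- left-skewed: about 19 to 22%, so the high value is mostly lost.

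Subjects with both excursions, per analyte:

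- variation unchanged: 0 to 0.4%, or at most 90 × 0.004 = 0.36 per arm;
- within-subject SD raised 1.5-fold: about 0.05%, 1.8% and 6.8% at within-subject shares 0.3, 0.6 and 0.9, or about 0.05, 1.6 and 6 per arm.

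Share of all subjects with any low value whose low is hidden: 0 to 4% with unchanged variation, and up to 21% in the most extreme case (log SD 0.6, share 0.9, SD raised 1.5-fold).

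**The case against.** The strongest reply is that little is lost and most of it is visible elsewhere. The protocol (Section 9.3.4.5) asks only for changes from baseline by treatment and visit, and the SAP provides them; the shift table is an extra. Every out-of-range value is listed. A neutrophil count of 1.2, as in Step 1, is below the Table 5 cut-off of 1.5 ×10⁹/L and enters the PCS counts and listing. Clinically significant laboratory values are reported as adverse events (SAP 6.4.2.4) and tabulated by subject incidence over the treatment-emergent period (SAP 7.5.1). This stands. A reader might infer that the shift table is the only any-time laboratory summary, or that analytes missing from Table 5 have no other categorical summary. The adverse event tables rule out both readings.

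A reader might also infer that low values are mostly lost across all two-sided analytes. The documents give no reference ranges or distributions to support that, and Step 3 shows that the direction depends on skewness. Sodium, potassium and calcium should not be cited as analytes that lose lows in particular.

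A gap remains. PCS counts are by visit, and under SAP 7.1.2 a scheduled result displaces an unscheduled one in the same window. Calcium, glucose, magnesium, bicarbonate and albumin are measured but have no entry in Table 5. A low value that misses a PCS cut-off, or has none, and is not judged clinically significant has no any-time count by arm outside this table. Listings show such values but do not give incidence.

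**Conclusion.** The point holds in a limited form. That a two-directional subject appears in one direction only follows from the wording of SAP 7.5.4 and needs no assumption. The table can therefore undercount shifts to Low or to High. Which direction suffers depends on the analyte: usually Low where values are right-skewed with a lower limit near zero, about equally for symmetric analytes, and mostly High for left-skewed ones.

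The likely size is small. With ordinary within-subject variation, fewer than one subject per arm per analyte would be affected. The loss reaches several subjects per arm only if variation rises markedly on study and most of it is within subjects. All sizes rest on assumed ranges, SDs and shapes. This is a minor, inexpensive improvement to a descriptive safety display and has no bearing on the efficacy analyses.

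**What to change.** In SAP 7.5.4, for analytes with limits in both directions, replace the single worst-value table with two: shift from the baseline category to the lowest post-baseline value, and shift from the baseline category to the highest. Classify every subject in both. This makes shift to Low and shift to High subject incidences in their own right, and removes both the dependence on raw distance and the need for a tie rule. It uses data already collected. The cost is a change of SAP wording, some programming, and longer tables.
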